9.7. Vital Signs and Physical Evaluations

Vital sign measurements included oral temperature, pulse, systolic blood pressure, and diastolic blood pressure. Vital signs will be summarized at admission (Day -1), Day 1 pre-dose (Baseline), 1-hour post-dose, 2 hours post-dose, 4 hours post-dose, 5 hours post-dose, 6 hours post-dose, 8 hours post-dose, 12 hours post-dose, 16 hours post-dose, 24 hours post-dose, 36 hours post-dose, Day 3, Day 4, Day 5 and Day 12. Vital signs will be tabulated by visit and impairment group ([Table 129](#) through [Table 137](#); and [Listing 12](#)).

Physical Examinations performed at admission and Day 12. The following body systems will be assessed: Abdomen, Cardiovascular/heart Extremities, General Appearance, HEENT, Lymph nodes, Musculoskeletal, Neck, Neurological, Pulmonary/Chest, and Skin ([Listing 13](#)). A summary of abnormal physical exam findings

will be shown in [Table 138](#). Weight will be summarized at admission (Day -1), Day 1 pre-dose (Baseline), 1-hour post-dose, 2 hours post-dose, 4 hours post-dose, 5 hours post-dose, 6 hours post-dose, 8 hours post-dose, 12 hours post-dose, 16 hours post-dose, 24 hours post-dose, 36 hours post-dose, Day 3, Day 4, Day 5 and Day 12. Weight will be tabulated by visit and impairment group ([Table 139](#)).

9.8. Concomitant Medications

Concomitant medications will be coded to the Anatomical Therapeutic Classification using the WHO Drug Dictionary. The use of prior and concomitant medications taken during the study will be recorded on the CRFs. A by-subject listing of concomitant medication use will be presented ([Listing 14](#)). The use of concomitant medications during the study will be summarized by ATC1, ATC2 code and impairment group for the Safety population ([Table 140](#)).

9.9. Other Safety Measures

ECG intervals (RR, QRS, QT, QTcF, PR and ventricular rate) will be summarized at the day of admission and Day 12 using descriptive statistics ([Table 141](#); [Table 142](#); [Table 143](#); [Table 144](#); [Table 145](#); and [Table 146](#)). The proportion of subjects with bradycardia, tachycardia, conduction system disease (e.g., prolongation of the PR Interval, bundle branch block, fascicular block), arrhythmia (e.g., atrial fibrillation, atrial flutter, premature atrial/ventricular contractions, ventricular tachycardia), and Brugada pattern will be summarized by hepatic impairment group ([Table 147](#)). Individual overall interpretation and comments will be provided in [Listing 20](#). Individual ECG interval measurements will be provided in [Listing 21](#).

10. PHARMACOKINETICS

Pharmacokinetic (PK) analyses will be performed using noncompartmental analysis (NCA). PK concentrations and noncompartmental parameters will be summarized by impairment group. Statistics include the arithmetic mean, geometric mean (GM), standard deviation (SD), coefficient of variation (CV), minimum (min), maximum (max), and median. PK parameters ($AUC_{0-\text{last}}$, $AUC_{0-\infty}$, and C_{\max}) will be compared between impairment groups using ANOVA models with or without random effects. T_{\max} will be compared using 90% confidence intervals calculated using the inverted rank score method. Concentrations below the quantitation limit (BQL) prior to first measurable concentration will be imputed as zero.

10.1. Summary of Pharmacokinetic Sampling and Sample Properties

Samples with bioanalytical errors reported by the laboratory will be excluded. Collection times of samples missing the actual collection time will be imputed using the nominal collection time. Such samples will be identified in the analysis report ([Listing 22](#)).

10.2. Pharmacokinetic Analysis

10.2.1. Concentration Summaries

Drug plasma concentrations will be listed by impairment group, and subject, out of sample time window, and PK analyses-excluded samples indicated ([Listing 22](#)). The listings will also indicate the nominal and actual time associated with the sample (nominal time is defined as the time in hours since the first dose).

Potentially important bioanalytical errors and their effect on the PK analysis will be discussed.

Plasma drug concentrations will also be summarized by impairment group ([Table 148](#); [Table 149](#); [Table 150](#); and [Table 151](#)) and plotted.

- [Figure 26](#); [Figure 27](#); [Figure 28](#); and [Figure 29](#) (linear) and [Figure 33](#); [Figure 34](#); [Figure 35](#); and [Figure 36](#) (semilogarithmic) will plot all subject plasma PK profiles together by impairment group, as linear and semilogarithmic plots.
- Linear plots of subjects with hepatic impairment with their matched control ([Figure 30](#); [Figure 31](#); and [Figure 32](#)).
- Linear plots of plasma mean concentration curves will be shown in [Figure 37](#), with error bars representing ± 1 standard deviation.
- Semi-logarithmic plots of geometric mean plasma concentration curves will be shown in [Figure 38](#).

10.2.2. Pharmacokinetic Parameters

NCA PK parameters will be calculated using actual post-dose time. Samples with concentrations greater than the LLOQ will be considered for the estimation of λ_z . This slope will be computed from log-transformed concentration data. The correlation between time and concentration in the time points used to estimate λ_z should be sufficiently high ($R^2_{\text{adjusted}} > 0.9$ for λ_z) to be estimated reliably. At least three samples will be used for the calculation of λ_z . The range of selected time points should include all timepoints post 12 hours inclusive if appropriate.

Samples used to calculate λ_z along with the number of samples used for the calculation will be included in subject listings ([Listing 22](#)).

The AUC will be computed using the linear-up log-down (linear-log) trapezoidal method in WinNonlin (Pharsight Corporation, Cary, NC).

All PK parameters will also be summarized by impairment group using descriptive statistics ([Table 152](#); [Table 153](#); [Table 154](#); and [Table 155](#)). Additionally, subject-level PK parameters will be presented by participant in the table in the final report.

The following parameters will be estimated: C_{max} , T_{max} , $t_{(1/2)}$, $AUC_{(0\text{-last})}$, $AUC_{(0\text{-}\infty)}$, CL/F and V_d/F . See Section [3.3](#) for parameter definitions.

10.3. Comparison of Impairment Groups

If at least one matching participant in the healthy volunteer group is available in the impairment groups, the following random effects ANOVA model will be used to test for a group by site interaction and if significant ($p<0.10$), estimate group and site level parameters and compare impairment groups for primary PK parameters:

$$Y_{ij} = \mu + \tau_{[ij]} + \alpha_i + \gamma_k + \tau_{[ij]}\gamma_k + \varepsilon_{ij}.$$

Here, i represents the matched block, j represents the participant in matched block i , Y_{ij} is the log-transformed PK parameter for participant j in block i , $\tau_{[ij]}$ is the impairment group effect for the group in which participant j in block i belongs, α_i is the random group effect for matched block i , γ_k is the indicator variable for the fixed effect of study site k , and $\tau_{[ij]}\gamma_k$ is the interaction between subject impairment group and site. If no matching participants are available with PK parameters, the standard fixed effects ANOVA model without random effect α_i will be used. The following SAS code may be used to estimate the model above:

```
proc mixed data=impairment;
  class match group (ref="Matched Control") site;
  model logPKpar = group site group*site / solution cl alpha=0.10;
  random match;
  lsmeans group site group*site;
  run;
```

The estimates from this model can be exponentiated to get fold differences.

If the group by site interaction is not significant then the following model will be used to estimate group level parameters:

$$Y_{ij} = \mu + \tau_{[ij]} + \alpha_i + \gamma_k + \varepsilon_{ij}$$

The following SAS code may be used to estimate the model above:

```
proc mixed data=impairment;
  class match group (ref="Matched Control") site;
  model logPKpar = group site / solution cl alpha=0.10;
  random match;
  lsmeans group;
```

run;.

The estimates from this model can be exponentiated to get fold differences.

Pairwise fold differences in drug exposure will be calculated to compare each of the mild, moderate, and severe impairment groups with non-hepatically impaired controls. Fold difference and mean will be estimated by ANOVA and shown using 90% confidence intervals. An adjustment to the confidence level for multiple comparisons is not planned ([Table 156](#)).

T_{max} will be summarized in each impairment group using the median, and group differences will be assessed using nonparametric confidence intervals computed using the inverted rank score method ([Table 157](#)). Medians and confidence intervals will also be computed for each site. If the confidence intervals do not overlap between sites, then the T_{max} will also be summarized by site.

Summary box plots of PK parameters by impairment group (and site if appropriate) will also be prepared ([Figure 39](#); [Figure 40](#); [Figure 41](#); [Figure 42](#); [Figure 43](#); and [Figure 44](#)).

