3 STUDY DESIGN, OBJECTIVES AND ENDPOINTS OR OUTCOME MEASURES

3.1 Study Design Description

This is a Phase 1, single dose (200 mg), open-label, study comparing the pharmacokinetics and safety of Pretomanid in subjects with mild, moderate, and severe hepatic impairment relative to matched non-hepatically impaired subjects.

This study will enroll approximately 6 subjects with mild hepatic impairment (Child-Pugh A), approximately 6 subjects with moderate hepatic impairment (Child-Pugh B), approximately 6 subjects with severe hepatic impairment (Child-Pugh C), and approximately 18 matched non-hepatically impaired subjects. Subjects with moderate hepatic (Child-Pugh B) and severe hepatic impairment (Child-Pugh C) will be enrolled simultaneously following enrollment of subjects with mild impairment. An interim safety analysis of data for the first 3 hepatic impairment subjects' data will be performed in between the mild hepatic impairment group and the moderate and severe hepatic groups (Child-Pugh B and Child-Pugh C). A second interim safety analysis will be performed after the first 3 subjects are enrolled in the moderate or severe hepatic groups. If enrollment into the severe hepatic impairment group (Child-Pugh C) is completed before that of the moderate hepatic impairment group (Child-Pugh B), results from the Child-Pugh C cohort will be analyzed to determine the impact of severe hepatic impairment on the PK of Pretomanid and the need to continue enrollment of persons with moderate hepatic impairment (Child-Pugh B) will be reevaluated to determine whether the objectives of the study have been met.

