10.6.4 Primary PK Analysis

All PK parameters will be estimated through a non-compartmental analysis using a validated installation of WinNonlin version 6.3 or later. The recorded true time points will be used for PK calculation. Estimated total plasma PK parameters will include the following:

- AUC(0-∞): Area under the concentration time-curve extrapolated to infinity
- AUC(0-last): Area under the concentration time-curve to the last concentration above the lower limit of quantitation
- Cmax: Maximum concentration
- Tmax: Time of maximum concentration
- t(1/2): Apparent terminal elimination half-life
- CL/F: Apparent oral clearance calculated from Dose/AUC(0-∞)

- Vd/F: Apparent Volume of Distribution

Details of the statistical analysis will be included in the statistical analysis plan and may not be limited to the following: Hepatic impairment group means of drug exposure will be estimated through analysis of variance (ANOVA) models with impairment group as a fixed effect for the log-transformed estimated parameters. If the PK analysis set contains a matched control for each participant in all impairment groups, correlation between these matched pairs will be incorporated into the ANOVA model. Pairwise fold differences in drug exposure will be calculated to compare each of the mild, moderate, and severe impairment groups with non-hepatically impaired controls. Fold differences will be estimated using 90% confidence intervals. Tmax will be summarized in each group using the median and range, and group differences will be assessed using nonparametric confidence intervals.

Linear and semilogarithmic concentration-time profiles will also be plotted by impairment and non-hepatically impaired groups. Calculated PK parameters will be summarized using standard summary statistics (such as mean, median, standard deviation, coefficient of variation, or range) by impairment and non-hepatically impaired groups.

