4. INVESTIGATIONAL PLAN

4.1. Overall Study Design and Plan

Approximately 6 subjects will be enrolled in each of the hepatic impairment groups (Mild, Moderate and Severe), and approximately 18 non-hepatically impaired subjects will be enrolled as matched controls.

Subjects with hepatic impairment from all three groups will be enrolled starting with subjects who have mild hepatic impairment. Subjects with moderate and severe hepatic disease will be enrolled simultaneously. If enrollment into the severe hepatic impairment group is completed before that of the moderate hepatic impairment group, results from the severe cohort will be analyzed to determine the impact of severe hepatic impairment on the PK of Pretomanid and the need to continue enrollment of persons with moderate hepatic impairment will be reevaluated to determine whether the objectives of the study have been met. Non-hepatically impaired subject matches will be dosed only after the corresponding subject with hepatic impairment has completed the 36-hour blood sampling procedure. The group of up to 18 matched controls will be matched to the 18 subjects with hepatic impairment based on age (\pm 10 years) and body weight at screening (\pm 20% body weight). A control subject may be matched to more than one hepatic impairment subject if warranted, and if the subjects to which they are matched are not in the same disease severity group. Control subjects may be matched to hepatically impaired subjects at any site. Therefore, there may be less than 18 subjects with normal hepatic function ([Table 1](#); [Figure 2](#)).

Subjects will receive a single oral dose of Pretomanid 200 mg taken with 240 mL of water after overnight fast.

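### SAP 10.3 lets a group-by-site test at p<0.10 choose the model for each primary PK fold difference, and does not say which model gives the overall result once the test triggers.

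*SAP*

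**What the plan says.** SAP 10.3 sets out two models for the log-transformed PK parameters. The first has impairment group, site and their interaction as fixed effects and matched block as random; it "will be used to test for a group by site interaction and if significant" at p<0.10, to give estimates at group and site level. The second drops only the interaction: "If the group by site interaction is not significant then the following model will be used to estimate group level parameters", with the sample code line "model logPKpar = group site / solution cl alpha=0.10". If no matched participants have PK parameters, the SAP uses "the standard fixed effects ANOVA model without random effect" for the block. Site therefore stays in every version.

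SAP section 10 names AUC(0-last), AUC(0-∞) and Cmax as the parameters compared by ANOVA. The Table 156 shell shows its site column only when the interaction has p<0.10, but always lists Overall rows with a fold change for each impaired group.

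On recruitment, SAP 4.1 states: "Control subjects may be matched to hepatically impaired subjects at any site". Matching is on age and weight only, and neither document sets a same-site rule or a control quota per site. Protocol 3.1 says moderate and severe subjects "will be enrolled simultaneously following enrollment of subjects with mild impairment". The SAP version history records that the second site was added after SAP version 1.0.

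**The concern.** The model behind the primary fold difference is picked by a significance test on the same data. It is picked separately for three correlated parameters, in groups of about 6 split over two sites. Three things follow.

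- A chance result below 0.10 adds site-specific fold differences that look like findings. They appear only when the sites happen to disagree, so their nominal 90% intervals no longer have 90% coverage.
- The three parameters can be reported from different models. Table 156 has one site column for all three, with no rule for the case where only one triggers.
- Once the test triggers, the model behind the Overall rows is not stated. The sample code requests group least-squares means from the interaction model, so that is the likely reading. Those means cannot be estimated when a group has no subjects at one site.

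SAP 6.4 says the study is not powered for formal subgroup analyses and that none will be explored. A split by site conditional on a p-value sits badly with that.

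**Working it through.** **Inputs.** CV 25%, an observed two-fold difference, no correlation within matched pairs, and a 90% CI of (1.55, 2.59) (Protocol 10.3, SAP 5). Six severe subjects and about 18 controls (SAP 4.1). Two sites (SAP 6.7). Neither document gives numbers per site, so every split below is an assumption, written Duke/St. Louis. Block variance is set to zero, following the plan's own no-correlation assumption.

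**Reproducing the planned interval.** SD on the log scale = √ln(1 + 0.25²) = 0.2462. With 6 v 6, SE = 0.2462 × √(1/6 + 1/6) = 0.1422 and t(0.95, 10 df) = 1.812. Then 2 × exp(±1.812 × 0.1422) = (1.55, 2.59), which agrees.

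**All 18 controls, group only.** SE = 0.2462 × √(1/6 + 1/18) = 0.116; 32 df, t = 1.694; 90% CI (1.64, 2.43).

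**Cost of the site main effect.** The variance of severe versus control becomes σ² × (1/6 + 1/18 + d²/W). Here d is the difference between the severe and control groups in the fraction at St. Louis, and W is the sum over all groups of n × p × (1 − p), with p the fraction at St. Louis.

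| Split: controls; mild; moderate; severe | d | W | SE | 90% CI |
|---|---|---|---|---|
| 9/9; 3/3; 3/3; 3/3 | 0 | 9 | 0.116 | 1.64-2.43 |
| 15/3; 5/1; 4/2; 1/5 | 2/3 | 5.5 | 0.136 | 1.59-2.52 |
| 15/3; 6/0; 3/3; 0/6 | 5/6 | 4 | 0.155 | 1.54-2.60 |
| 18/0; 6/0; 3/3; 0/6 | 1 | 1.5 | 0.232 | 1.35-2.96 |
| 18/0; 6/0; 6/0; 0/6 | 1 | 0 | not estimable | none |

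For the third row: 1/6 + 1/18 + (5/6)²/4 = 0.396, and 0.2462 × √0.396 = 0.155.

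**By-site intervals after a trigger** (28 df, t = 1.701). With 3 severe and 9 controls at a site, SE = 0.2462 × √(1/3 + 1/9) = 0.164, giving (1.51, 2.64). With 1 severe and 9 controls, SE = 0.2462 × √(1 + 1/9) = 0.260, giving (1.29, 3.11).

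**False triggers.** The test has 3 interaction df and 28 residual df. With no true interaction, simulation (40,000 trials) gives 10% per parameter. At least one of the three triggers in about 16% of trials (assumed correlations: 0.98 between the AUCs, 0.85 between AUC and Cmax), 19% (0.98 and 0.5) or 20% (0.95 and 0.6). If independent, 1 − 0.9³ = 27%.

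**After a chance trigger, balanced sites.** The median ratio between the two site-specific severe fold differences is 1.37, and the nominal 90% by-site interval covers about 71%.

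**Power of the switch.** With balanced sites and a severe fold difference that truly differs 1.5-fold between sites, the test triggers only about 40% of the time.

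**Empty cells.** With no controls at St. Louis (18/0; 5/1; 3/3; 1/5), the main-effects model still gives SE 0.164 and (1.52, 2.64). The overall severe-versus-control contrast from the interaction model is not estimable. The same holds with 9/9 controls if severe is 0/6.

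**The case against.** The strongest reply is that site belongs in the model. A reader might infer that the SAP contradicts the protocol, since Protocol 10.6.4 describes "analysis of variance (ANOVA) models with impairment group as a fixed effect for the log-transformed estimated parameters" and does not mention site. The documents do not support that: the same section leaves details to the SAP and says they may go beyond what is listed. A reader might also infer that the site term creates confounding between group and site. It does not. Unbalanced recruitment creates the confounding, and the term guards against it.

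Dropping site from the primary model would carry its own risk. In the 15/3; 6/0; 3/3; 0/6 split, an assumed true site ratio of 1.2 makes a group-only model estimate a true two-fold difference as 2 × 1.2^(5/6) = 2.33. Its simulated 90% coverage is then about 66%, against about 90% for group + site. The site-adjusted interval in that split, (1.54, 2.60), is also no wider in practice than the planned (1.55, 2.59). All of this stands.

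It is also true that the rule is pre-specified, that the aim is estimation, that Table 156 keeps Overall rows, and that severe imbalance is speculative. Protocol 2.2.2 expects impaired subjects from both institutions and controls from site-specific registries, and Protocol 10.5.1 lets mild enrolment continue during the first safety review. These points limit how likely the worst layouts are. They do not repair the coverage of the by-site intervals or say which model produces the Overall rows.

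**Conclusion.** The point holds for the p<0.10 switch and the undefined Overall estimate, and not for the site main effect. The 10% false-trigger rate per parameter follows from the test level. The rate for any of the three depends on correlations the documents do not give: 16-20% under the values assumed, 27% at independence. The coverage of about 71% assumes balanced sites, no true interaction and no block variance. Non-estimability of the overall contrast from the interaction model needs only an empty site cell in the severe or control group, which the any-site matching rule allows but does not make likely.

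The precision cost of the site term is conditional: nothing when sites are balanced, and a 33% larger SE in the 15/3; 6/0; 3/3; 0/6 split (0.155/0.116). The main-effects contrast is lost completely only if no group is recruited at both sites and the severe and control groups sit at different sites. The documents allow a range for this cost, not one figure.

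**What to change.** In SAP 10.3:

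1. Remove the p<0.10 switch.
2. Use one model, with group and site fixed and matched block random, for the primary Overall fold differences of AUC(0-last), AUC(0-∞) and Cmax, whatever the interaction p-value. State in the Table 156 shell that the Overall rows come from it.
3. Present by-site estimates as descriptive only, for impaired groups that have both impaired subjects and controls at that site.
4. Report the group-only model as a sensitivity analysis, to be relied on if group and site are completely aliased, with that confounding stated.

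The cost is SAP wording and one table shell, with no new data; Protocol 10.1 requires the SAP to be final before database lock. The downside is that a true group-by-site interaction would be described rather than modelled in the primary estimate. With about 40% power for a 1.5-fold difference between sites, the present switch would often miss one.

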Non-hepatically impaired subjects in the control group will be matched to hepatically impaired subjects by age (± 10 years) and screening body weight ($\pm 20\%$) consistent with previous studies on hepatic impairment with matched controls (15-17). A control subject may be matched to more than one hepatic impairment subject if warranted (e.g., lack of sufficient enrollment of non-hepatically impaired subjects) and if the subjects to which they are matched are not in the same disease severity group. In this case the control subject would participate in the study one time but be matched to more than one subject with hepatic impairment. If subjects in either the hepatically impaired or non-hepatically impaired control groups withdraw from the study prior to completion of Day 5 (Visit 04) when the last PK samples are obtained, the subject may be replaced. At screening, the subjects will be categorized, into one of the following 4 groups as described in [Table 4](#).

Table 4: Study Groups

Study Group	Severity	N
Group 1	Child-Pugh A = 5 to 6 points (Mild)	6
Group 2	Child-Pugh B = 7 to 9 points (Moderate)	6
Group 3	Child-Pugh C = 10 to 15 points (Severe)	6
Group 4	Non-hepatically impaired controls	18

A detailed schedule of assessments is shown in [Appendix A](#). The study will consist of the following:

- Screening period (Day -22 to Day -2) will occur between 1 and 21 days before admission to the confinement/hospital unit clinic (Day -1).
- Study product will be administered on Study Day 1.
- An approximately 36-hour – 60 hour confinement/hospitalization period that includes intensive PK sampling from Study Day 1 through Study Day 2 (36-hour sample) or Day 3 depending on site preference.
- Visits on Study Days (3), 4, and 5 for medical/surgical history and concomitant medications review, safety laboratory testing (Study Day 5), assessment of vital signs, PK sampling, and SAE/AE assessment, and on Study Day 12 for final study procedures (review of medical/surgical history and concomitant medications, assessment of vital signs, testing for coagulation and pregnancy, urinalysis, physical exam, ECG, safety laboratory testing and SAE/AE assessment).

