4.4.3. Method of Assigning Subjects to Treatment Groups (Randomization)

There is no randomization performed for this study. Subjects are assigned to the 3 hepatically impaired groups based on the Child-Pugh score, with approximately 6 subjects in each of the hepatic impairment groups (Groups 1, 2, and 3) and approximately 18 non-hepatically impaired subjects in Group 4.

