Table 156: Estimated Impairment Group Fold Change for Noncompartmental PK Parameters
(continued)

Site	Impairment Group	Statistic	AUC _{0-last} (ng·hr/mL)	AUC _{0-∞} (ng·hr/mL)	C _{max} (ng/mL)
		90% CI of Mean			
	Moderate	Mean			
		90% CI of Mean			
		Fold Change ^a			
		90% CI of Mean			
	Severe	Mean			
		90% CI of Mean			
		Fold Change ^a			
		90% CI of Mean			
	Matched Controls	Mean			
		90% CI of Mean			

^a Comparison is to matched controls

Table 157: Estimated Impairment Group Shift for Noncompartmental PK Parameters

[Implementation Note: Site column will only be included if confidence intervals between sites do not overlap.]

Site	Impairment Group	Statistic	T _{max} (h)
Duke	Mild	Median	
		90% CI ^a	
		Shift ^b	
		90% CI ^a	
	Moderate	Median	
		90% CI ^a	
		Shift ^b	
		90% CI ^a	
	Severe	Median	
		90% CI ^a	
		Shift ^b	
		90% CI ^a	
Saint Louis	Matched Controls	Median	
		90% CI ^a	
	Mild	Median	
		90% CI ^a	
		Shift ^b	
		90% CI ^a	
	Moderate	Median	
		90% CI ^a	
		Shift ^b	
		90% CI ^a	
	Severe	Median	
		90% CI ^a	
Matched Controls		Shift ^b	
		90% CI ^a	
Matched Controls	Median		
		90% CI ^a	

Table 157: Estimated Impairment Group Shift for Noncompartmental PK Parameters (continued)

Site	Impairment Group	Statistic	T _{max} (h)
Overall	Mild	Median	
		90% CI ^a	
		Shift ^b	
		90% CI ^a	
	Moderate	Median	
		90% CI ^a	
		Shift ^b	
		90% CI ^a	
	Severe	Median	
		90% CI ^a	
		Shift ^b	
		90% CI ^a	
	Matched Controls	Median	
		90% CI ^a	

^a Confidence limits will be estimated using the inverted rank score method.

^b Comparison is to matched controls

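### Table 157 plans 90% intervals for by-site T_max medians that cannot reach 90% coverage in any site-by-group cell with fewer than 5 subjects, and the non-overlap trigger for showing them is unsuitable

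*SAP*

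**What the plan says.** SAP 10 states that T_max will be compared using 90% confidence intervals "calculated using the inverted rank score method". SAP 10.3 describes a summary by impairment group and then adds: "Medians and confidence intervals will also be computed for each site". A by-site summary follows "If the confidence intervals do not overlap between sites".

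The implementation note to Table 157 repeats the condition: "Site column will only be included if confidence intervals between sites do not overlap". When the condition is met, the shell crosses site (two sites plus Overall) with impairment group. Each cell has a median with a 90% CI, and each impaired group also has a shift against controls with a 90% CI. The footnote applies to both kinds of interval: "Confidence limits will be estimated using the inverted rank score method". Neither place sets a minimum cell size or a fallback.

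SAP 4.4.3 gives the group size as "approximately 6 subjects in each of the hepatic impairment groups (Groups 1, 2, and 3". SAP 6.7 names two sites. The documents do not say how each group divides between them.

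**The concern.** A rank-based interval has only a few possible coverage levels, and in a very small sample even the widest finite one may fall short of 90%. Splitting groups of about 6 over two sites produces such samples. Inverting strictly at 90% would then give an unbounded interval or none. If software prints minimum to maximum instead, the column header overstates its coverage.

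The trigger raises a separate question. It decides whether the site rows appear by comparing site intervals, but the sentence does not say whether these are computed within impairment group or over all subjects at a site. At stake is how a reader would interpret any apparent site difference in T_max, and whether the printed 90% labels can be trusted.

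**Working it through.** **The plan's own precision figure.** The only one is for exposure, not T_max (SAP 5): 90% CI (1.55, 2.59) for an observed two-fold difference with a CV of 25% and no pair correlation. With s = √ln(1 + 0.25²) = 0.246 and 6 per group, 2·exp(± t(0.95; 10 df)·s·√(1/6 + 1/6)) gives (1.546, 2.588), so the figure reproduces. The plan gives no figure for T_max.

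**Inputs.** Level 90% (SAP 10); about 6 per impaired group (SAP 4.4.3); two sites (SAP 6.7). The split by site is not given, so every split of 6 is examined.

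**Interval for one median.** For a continuous variable, minimum to maximum covers 1 − 2(1/2)^n. Inverting the sign test and inverting the signed-rank test (which also assumes symmetry) have this same ceiling.

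- n = 1: 0%
- n = 2: 50%
- n = 3: 75% (a simulation check gave 74.9%)
- n = 4: 87.5%
- n = 5: 93.75%
- n = 6: 96.9%

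So 90% needs n of at least 5. For a group of 6:

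- 3/3: 75% and 75%; both cells fail.
- 4/2: 87.5% and 50%; both fail.
- 5/1: 93.75% and 0%; one fails.
- 6/0: 96.9% and an empty cell; none fails.

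Over the three impaired groups, the number of affected cells runs from 0 (each group at a single site) to 6 (every group split 3/3 or 4/2). A group somewhat larger than 6 does not escape: up to 9 subjects, the smaller of two site cells holds at most 4, with a ceiling of 87.5%.

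**Shift interval.** With m impaired and n control subjects, maximum coverage is 1 − 2/C(m+n, m). If controls divide evenly there are about 9 per site.

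- 3 v 9: 1 − 2/220 = 99.1%
- 2 v 9: 1 − 2/55 = 96.4%
- 3 v 3: 1 − 2/20 = 90%
- 1 v 9: 1 − 2/10 = 80%
- 2 v 4: 1 − 2/15 = 86.7%

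Most of these are attainable. The exceptions are single-subject cells and cells with few controls.

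**Overall rows.** At n = 6, minimum to maximum covers 96.9%; the next narrower interval covers 1 − 14/64 = 78.1%. At n = 18, the 6th to 13th ordered values cover 90.4%. Intervals of at least 90% exist, but the attained level differs by group.

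**Trigger, pooled over groups.** This was simulated with no site effect, assuming lognormal T_max (median 4.5 h, log-SD 0.4; 4,000 runs). Site mixes are given as mild, moderate, severe, control. With no group difference and a balanced mix, the trigger fires in 1.9% of runs. With T_max assumed 1.5 times longer in moderate and 2 times longer in severe impairment:

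- (3, 3, 3, 9) at both sites: 0.8%
- (6, 2, 1, 9) v (0, 4, 5, 9): 6.1%
- (6, 1, 0, 14) v (0, 5, 6, 4): 21%

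With T_max rounded to nominal sampling times, the same three become 0.2%, 2.3% and 9.6%.

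**Trigger, within group.** With minimum-to-maximum intervals, continuous times and no site effect, complete separation at 3/3 has probability 2/C(6,3) = 10% per group, and 1 − 0.9³ = 27% for at least one of three groups.

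**The case against.** The by-site rows are conditional and additional. The Overall rows remain, and the protocol (10.6.4) asks only for group-level T_max summaries and nonparametric intervals for group differences. T_max takes few distinct values at the scheduled sampling times, and ties can raise actual coverage above the continuous-case figures. These points stand and limit the importance of the defect. They do not make 90% attainable in a small cell, because ties cannot be relied on to supply the missing coverage.

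A within-group reading of the trigger is also plausible, since SAP 10.3 begins with impairment groups and Table 157 crosses site with group. On that reading the case-mix objection falls away, but the trigger then depends on the small-cell intervals. Case mix also matters only if T_max differs by group, which the documents do not establish. The 21% figure belongs to an extreme imbalance under assumed effects.

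A reader might draw four stronger conclusions that the documents do not support:

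- *That at least three cells must always be mislabelled.* A group enrolled at one site leaves an empty cell, not a mislabelled one, so the floor is zero.
- *That all by-site intervals are invalid.* Control cells of adequate size, cells of 5 or more and most shift intervals can reach 90%.
- *That the trigger is a 2% test at odds with the 10% rule for AUC and C_max.* The 2% comes from equal-SE normal intervals (z = 2 × 1.645/√2 = 2.33). The 10% rule is a group-by-site interaction test that selects a model, whereas the T_max rule only decides on a display.
- *That the primary outcome is compromised.* The stated primary outcome measure is total plasma concentration. T_max is one of seven parameters derived from it, and its Overall comparison is unaffected.

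**Conclusion.** The point holds for medians in the conditional site-by-group cells. Below 5 subjects a finite 90% rank interval does not exist. With 6 per impaired group, this affects at least one cell of every group enrolled at both sites, and both cells under 3/3 or 4/2 splits. The coverage ceilings are exact for a continuous variable; the number of affected cells depends on the unstated site split.

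The trigger is unsuitable under either reading, and the SAP does not say which applies. The size of the case-mix problem rests on assumed group differences in T_max and assumed site mixes. Severity is low, because the branch is conditional and descriptive and the Overall results stand.

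**What to change.** - Remove the non-overlap rule from SAP 10.3 and the matching Table 157 note. Remove the box-plot references to site where appropriate (end of SAP 10.3, note to Figure 39) so far as they depend on it for T_max.
- Show site-by-group rows descriptively as n, median, minimum and maximum. This agrees with the median and range in protocol 10.6.4.
- Print a site-level 90% interval only where the cell sizes allow it: n of at least 5 for a median, and 1 − 2/C(m+n, m) of at least 0.90 for a shift.
- Keep the Overall rank-based intervals and state their attained coverage.

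The cost is SAP wording and a revised table shell, with no new data. The downside is that some conditional site-level intervals are no longer shown.
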